6.1.8.2 MANAGEMENT OF MOST COMMON SIDE EFFECTS SPECIFIC TO EACH TKI AGENT

Dose Reduction and Interruption Instructions for Lenvatinib

Table 1. Adverse Reactions Requiring Dose Modification of Lenvatinib

Adverse Reaction	CTCAE Grade	Action	Dose Reduce and Resume Lenvatinib
Hypertension	Grade 3 ¹	Hold	Resolves to Grade 0, 1, or 2
	Grade 4	Discontinue	Do Not Resume
Cardiac Dysfunction	Grade 3	Hold	Resolves to Grade 0, 1, or baseline
	Grade 4	Discontinue	Do Not Resume
Arterial Thrombotic Event	Any Grade	Discontinue	Do Not Resume
Hepatotoxicity	Grade 3 or 4	Hold OR Discontinue	Consider resuming at reduced dose if resolves to Grade 0-1 or baseline
Hepatic Failure	Grade 3 or 4	Discontinue	Do Not Resume
Proteinuria	Greater than or equal to 2 gm/24 hours	Hold	Resolves to less than 2 gm/24 hours
Nephrotic Syndrome	-----	Discontinue	Do Not Resume
Nausea, Vomiting, and Diarrhea ²	Grade 3	Hold	Resolves to Grade 0, 1, or baseline
Vomiting and Diarrhea ²	Grade 4	Discontinue	Do Not Resume
Renal Failure or Impairment	Grade 3 or 4	Hold OR Discontinue	Consider resuming at reduced dose if resolves to Grade 0-1 or baseline
GI Perforation	Any Grade	Discontinue	Do Not Resume
Fistula	Grade 3 or 4	Discontinue	Do Not Resume
QTc Prolongation	Greater than 500 ms	Hold	Resolves to less than 480 ms or baseline
Reversible Posterior Leukoencephalopathy syndrome	Any Grade	Hold OR Discontinue	Consider resuming at reduced dose if resolves to Grade 0 to 1
Hemorrhage	Grade 3	Hold	Resolves to Grade 0 to 1
	Grade 4	Discontinue	Do Not Resume

1: Grade 3 despite optimal anti-hypertensive therapy

2: Initiate prompt medical management for nausea, vomiting or diarrhea. Permanently discontinue for Grade 4 vomiting and diarrhea despite medical management

Other adverse reactions with Lenvatinib will be managed following the instructions from Table 2:

Table 2. Dose Modifications for Lenvatinib for treatment-related Persistent and Intolerable Grade 2 or Grade 3 Adverse Reactions or Grade 4 Laboratory Abnormalities^a

Adverse Reaction	Modification	Adjusted Dose ^b
First occurrence	Interrupt until resolved to Grade 0-1 or baseline	20 mg (two 10 mg capsules) orally once daily
Second occurrence ^c	Interrupt until resolved to Grade 0-1 or baseline	14 mg (one 10 mg capsule plus one 4 mg capsule) orally once daily

Third occurrence ^c	Interrupt until resolved to Grade 0-1 or baseline	10 mg (one 10 mg capsule) orally once daily
-------------------------------	---	---

a: Initiate medical management for nausea, vomiting, or diarrhea prior to interruption or dose reduction of Lenvatinib

b: Reduce dose in succession based on the previous dose level (24 mg, 20 mg, or 14 mg per day)

c: Refers to the same or a different adverse reaction that requires dose modification

Patients with confirmed systolic BP ≥140 mmHg or diastolic BP ≥90 mmHg will be administered antihypertensive agents and monitored every 1-2 weeks. In patients with systolic BP ≥160 mmHg or diastolic BP ≥100 mmHg despite optimal management the treatment dose will be reduced. Patients with confirmed proteinuria Grade ≥2 (1.0–3.4 g/24h) will be tested every 2 weeks; and treatment will be interrupted until proteinuria decreases to Grade 0–1 or baseline level at which time, a lower dose will be restarted.

For patients with DTC, the recommended dose of Lenvatinib is 14 mg taken orally once daily in patients with severe renal impairment (creatinine clearance [CLcr] less than 30 mL/min calculated by the Cockcroft-Gault equation) or severe hepatic impairment (Child-Pugh C)

Dose Reduction and Interruption Instructions for Sorafenib

Temporary interruption of Sorafenib is recommended in patients undergoing major surgical procedures.

Temporary interruption or permanent discontinuation of Sorafenib may be required for the following:

- Cardiac ischemia or infarction
- Hemorrhage requiring medical intervention
- Severe or persistent hypertension despite adequate anti-hypertensive therapy
- Gastrointestinal perforation
- QTc prolongation
- Severe drug-induced liver injury

Table 3. Recommended Doses for Patients with DTC Requiring Sorafenib Dose Reduction

Dose Reduction	Sorafenib Dose	
First Dose Reduction	600 mg daily dose	400 mg and 200 mg 12 hours apart (2 tablets and 1 tablet 12 hours apart – either dose can come first)
Second Dose Reduction	400 mg daily dose	200 mg twice daily (1 tablet twice daily)
Third Dose Reduction	200 mg daily dose	200 mg once daily (1 tablet once daily)

When dose reduction is necessary for dermatologic toxicities, reduce the Sorafenib dose as indicated in Table 4 below.

Table 4. Recommended Sorafenib Dose Modifications for treatment-related Dermatologic Toxicities

Dermatologic Grade	Toxicity	Occurrence	Sorafenib Modification	Dose
--------------------	----------	------------	------------------------	------

Permanently discontinue Cabozantinib for any of the following:

- Development of visceral perforation or fistula formation
- Severe hemorrhage
- Serious arterial thromboembolic event (e.g., myocardial infarction, cerebral infarction)
- Nephrotic syndrome
- Malignant hypertension, hypertensive crisis, persistent uncontrolled hypertension despite optimal medical management
- Osteonecrosis of the jaw
- Reversible posterior leukoencephalopathy syndrome

In Patients Concurrently Taking a Strong CYP3A4 Inhibitor:

Reduce the daily Cabozantinib dose by 40 mg (for example, from 140 mg to 100 mg daily or from 100 mg to 60 mg daily). Resume the dose that was used prior to initiating the CYP3A4 inhibitor 2 to 3 days after discontinuation of the strong inhibitor.

In Patients Concurrently Taking a Strong CYP3A4 Inducer:

Increase the daily Cabozantinib dose by 40 mg (for example, from 140 mg to 180 mg daily or from 100 mg to 140 mg daily) as tolerated. Resume the dose that was used prior to initiating the CYP3A4 inducer 2 to 3 days after discontinuation of the strong inducer. The daily dose of Cabozantinib should not exceed 180 mg

Dose Reduction and Interruption Instructions for Vandetanib

For treatment-related adverse reactions:

The 300 mg daily dose can be reduced to 200 mg (two 100 mg tablets) and then to 100 mg for Common Terminology Criteria for Adverse Events (CTCAE) Grade 3 or greater toxicities.

Interrupt Vandetanib for the following:

- Corrected QT interval, Fridericia (QTcF) greater than 500 ms: Resume at a reduced dose when the QTcF returns to less than 450 ms.
- CTCAE Grade 3 or greater toxicity: Resume at a reduced dose when the toxicity resolves or improves to CTCAE Grade 1.

For recurrent toxicities:

Reduce the dose of Vandetanib to 100 mg after resolution or improvement to CTCAE Grade 1 severity, if continued treatment is warranted.

Because of the 19-day half-life, adverse reactions including a prolonged QT interval may not resolve quickly. Monitor appropriately.

For patients with renal impairment:

Reduce the starting dose to 200 mg in patients with moderate (creatinine clearance ≥ 30 to < 50 mL/min) and severe (creatinine clearance < 30 mL/min) renal impairment.

For patients with hepatic impairment:

Vandetanib is not recommended for use in patients with moderate and severe hepatic impairment.

6.1.9 DURATION OF THERAPY

TKIs therapy (Lenvatinib, Sorafenib, Cabozantinib or Vandetanib) will be maintained until radiological disease progression is confirmed or earlier due to toxicity (see section 6.1.8).

6.1.10 TRACKING OF DOSE

Records of treatment compliance for each subject will be kept during the study through a pill diary which will be checked by the treating physicians or APPs at each visit

6.2 STUDY AGENT ACCOUNTABILITY PROCEDURES

6.2.1 Drug Accountability

Lenvatinib is purchased from Esai as a standard of care. Sorafenib is purchased from Bayer as a standard of care. Vandetanib is purchased from Sanofi Genzyme as standard of care. Cabozantinib is purchased from Exelixis as standard of care.

6.2.2 Treatment Compliance

Records of study medications used, dosages administered, and intervals between visits will be recorded by study personnel.

6.2.3 Biological sample accountability

Record of sample collection and processing will be kept in Moffitt Tissue Core Database and in the separate excel sheet. The database will include storage information in -80°C freezer. The tumor, plasma and PBMC samples will be released or further processed upon separate instructions from the principal investigator.

7. STUDY PROCEDURES AND SCHEDULE

7.1 STUDY PROCEDURES/EVALUATIONS

7.1.1 STUDY-SPECIFIC PROCEDURES

[figure not shown]
Study-specific procedures that are not part of standard clinical care include:

- Frequency of thyroglobulin and thyroglobulin antibodies monitoring.
- Tissue biopsy prior to the initiation of the TKI therapy, at 4 months and at 6 months.

7.1.2 STANDARD OF CARE STUDY PROCEDURES

Standard of care procedures obtained during the study:

- Medical history.
- Medication history.
- Physical examination.
- Radiographic or other imaging assessments. State the specific imaging required and, as

□

[Redacted text block]

[Redacted text block]

[REDACTED]

[REDACTED]

[REDACTED]

[REDACTED]

[REDACTED]

[REDACTED]

[REDACTED]

[REDACTED]

[REDACTED]

[REDACTED]

[REDACTED] be processed within 2 hours from collection.

[REDACTED]

[REDACTED]

[REDACTED]

[REDACTED]

[REDACTED]

[REDACTED]	[REDACTED]	[REDACTED]
[REDACTED]	[REDACTED]	[REDACTED]
[REDACTED]	[REDACTED]	[REDACTED]
[REDACTED]	[REDACTED]	[REDACTED]
[REDACTED]	[REDACTED]	[REDACTED]
[REDACTED]	[REDACTED]	[REDACTED]
[REDACTED]	[REDACTED]	[REDACTED]
[REDACTED]	[REDACTED]	[REDACTED]

7.3 STUDY SCHEDULE

7.3.1 SCREENING

Screening Visit (Day -28 to -0)

Before performing any procedures or assessments, the nature of the study and the potential risks associated with the trial will be explained to all subject candidates and written informed consent will be obtained. Once informed consent has been obtained (within 8 weeks of first dose of study drug), the following procedures and evaluations will be performed:

- Verify inclusion/exclusion criteria (See Sections 5.1-5.2)
- Record demographic data.
- Evaluate ECOG performance status (Appendix 2).
- Establish pTNM staging and diagnosis (Appendix 1).
- Record medical and surgical history.
- Obtain vital signs (systolic and diastolic BP, HR, RR, and body temperature), weight, and height. BP, HR, and RR will be obtained after subjects have been resting for 5 minutes. For subjects with an elevated BP ($\geq 140/90$ mmHg), confirmation should be obtained by performing 2 assessments 1 hour apart. Systolic BP ≥ 160 mmHg or diastolic BP ≥ 100 mmHg should be confirmed by repeat measurements after an hour.
- Perform a comprehensive physical examination (including a neurological evaluation).
- Collect blood samples for laboratory testing and thyroid panel and pregnancy test if indicated (See Table 6 for the tests to be performed).
- Collect urine sample for dipstick testing (See Table 6 for the tests to be performed).
- Collect urine sample for β -hCG pregnancy testing from all women of childbearing potential.
- Perform targeted radiologic imaging studies, CT/MRI of head/neck/chest/abdomen/pelvis and other areas of known disease at screening plus any areas of newly suspected disease.
- Record all prior and concomitant medication use (prescription and nonprescription medications as well as transfusions).
- Plan for obtaining tumor tissue.

The screening form must be completed for all subjects screened, providing reasons for screen failure when applicable.

7.3.2 ENROLLMENT/BASELINE

Enrollment/Baseline: Cycle 0 Day -2 to Cycle 1 Day 1 (cycles are considered to last 28 days)

The baseline assessment can be performed on Cycle 1 Day 1 (C1D1), prior to treatment.

Clinical and laboratory assessments are valid if obtained within 72 hours of baseline assessment.

- Obtain informed consent or verify previously obtained during screening signed informed consent form.
- Verify inclusion and exclusion criteria.
- Obtain laboratory tests; urinary dipstick; and thyroid panel.
- Confirm negative urine/serum pregnancy test.
- Obtain demographic information, medical history, medication and social history.
- Evaluate ECOG performance status.
- Obtain vital signs.
- Record all concomitant medication use.
- Perform a comprehensive physical examination.
- Establish new baseline tumor assessments (selection of target and non-target lesions) based upon scans taken (CT and/or MRI) that showed evidence of disease progression (unless performed within 4 weeks).
- Verify that study participant received Lenvatinib/Sorafenib/Cabozantinib/Vandetanib through special pharmacy.
- Educate about potential AEs and SAEs. Encourage early recognition and reporting.
- Obtain tumor tissue (should be done prior to initiation of therapy).

7.3.3 FOLLOW-UP

Follow-up Visits

Study participants will be seen weekly for the first cycle (Cycle 1 Days 8, 15 and 22), every two weeks for the second cycle (Cycle 2 Days 1, 15), every four weeks until cycle 12 (Day 1 of Cycles 3-12); and every 2 cycles thereafter until end of study (Day 1 of cycles 14, 16, 18, 20 and 24). However, when the patient is off the TKI with observation only in the adaptive arm, the patient needs to follow up every 28 days (+/- 7 days) for determination of starting a new cycle.

In each scheduled visit we will:

- Obtain vital signs.
- Record all concomitant medication use.
- Perform a comprehensive physical examination.
- Evaluate ECOG performance status.
- Obtain laboratory tests and urinary dipstick.
- Assess for AEs and SAEs.
- Assess compliance with the medication.
- Assess survival.

Thyroid panel evaluation

Thyroid panel will be assessed every 2 weeks during the first two cycles (Cycle 1 Day 15, Cycle 2 Day 1, Cycle 2 Day 15, and Cycle 3 Day 1). If the tumor marker (thyroglobulin in DTC patients; calcitonin or CEA in MTC patients) drops by $\geq 50\%$ from baseline (Cycle 1 Day 1) during the first two cycles (analysis of Cycle 3 Day 1 included), the patient will be randomized to receive either standard (continuous) or adaptive (intermittent) therapy. Patients randomized to

the standard therapy arm will then get Thyroid panel checked every 3 cycles (Day 1 of Cycle 6, 9, 12). Patients randomized to the adaptive therapy arm will get Thyroid panel checked every cycle (Day 1) during the first two years. After 24 months, patients in the adaptive therapy regimen who remain on TKI therapy will be given the choice to continue with the adaptive therapy regimen and monitoring of the thyroid panel in every cycle; or to convert to standard (continuous) regimen in which case thyroid panel evaluation will be checked every 3 cycles. In either case, all patients that continue to receive TKI therapy beyond 24 months will be treated off trial. Patients in which the tumor marker does not drop $\geq 50\%$ within the first two months of TKI therapy will be managed by the standard of care.

Diagnostic imaging

Diagnostic imaging of affected and suspected sites (CT and/or MRI) will be done at Day 1 of cycles 3, 6, 9, 12, 16, 20, 24 in all patients. Diagnostic imaging will continue to be done every 4 months thereafter while the patient remains on TKI therapy or as clinically indicated otherwise.

7.3.4 FINAL STUDY VISIT

Final Study Visit

At the end of the study (at least 24 months after TKI initiation) the following data will be collected:

- Obtain vital signs.
- Record all concomitant medication use.
- Perform a comprehensive physical examination.
- Evaluate ECOG performance status.
- Obtain laboratory tests and urinary dipstick.
- Obtain thyroid panel (if not done within previous 3 weeks)
- Assess for AEs and SAEs.
- Assess compliance with the medication.
- Diagnostic imaging of affected and suspected sites (CT and/or MRI).
- Assess survival.

7.3.5 EARLY TERMINATION VISIT

An End of Treatment (EOT) visit will be performed for all subjects who do not complete the 24 month treatment period for any reason (e.g. disease progression, unacceptable toxicity, withdraw consent, etc.). At the end of treatment (30 days after last TKI dose, or any time within 30 days of being removed from treatment for patients in the adaptive therapy arm) the following data will be collected:

- Obtain vital signs.
- Record all concomitant medication use.
- Perform a comprehensive physical examination.
- Evaluate ECOG performance status.
- Obtain laboratory tests and urinary dipstick.
- Assess for AEs and SAEs.
- Assess compliance with the medication.

- Assess survival.

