5.4.2 HANDLING OF PARTICIPANT WITHDRAWALS OR TERMINATION

Every effort will be made to undertake protocol-specified safety follow-up procedures to capture AEs, serious adverse events (SAEs), and unanticipated problems.

Those who discontinue protocol therapy early will be followed for response until progression and for survival for 1 year from the date of withdraw or termination.

Patients removed from study for unacceptable adverse events will be followed until resolution or stabilization of the adverse event.

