- d: The baseline assessment can be performed on Cycle 1 Day (C1D1), prior to treatment. Clinical and laboratory assessments are valid if obtained within 72 hours of baseline assessment.
- e: For pTNM Staging see Appendix 1
- f: For ECOG assessments see Appendix 2.
- g: Assessments will include vital signs (resting BP, HR, RR, and body temperature, weight, and height. Height will be measured at the Screening Visit only. Elevated BP (Systolic BP \geq 140 mmHg and/or elevated Diastolic BP \geq 90 mmHg) should be confirmed by 2 assessments 1 hour apart. If systolic BP is \geq 160 mmHg or diastolic BP \geq 100 mmHg, BP should be confirmed by repeat measurements after an hour.
- h: Laboratory tests include: CBC w/differential, CMP, ALT, AST, magnesium, amylase, lipase, urine dipstick and if clinically indicated INR (see Table 6).
- i: Thyroid panel includes: TSH, free T4, and for patients with DTC thyroglobulin and thyroglobulin antibodies; and for patients with MTC calcitonin and CEA (see Table 6). Thyroid panel results may be collected up to 7 days prior to the first dose on Cycle 1 Day 1. These lab tests should be performed while the patient is in a fasting state.
- j: Serum or urine, in women of childbearing potential only.
- k: Baseline imagine to include CT/MRI of head /neck/chest/abdomen/pelvis and other areas of known disease. On treatment imagine will include only areas of known disease plus any areas of newly suspected disease.
- l: AEs/SAEs will be assessed during each visit clinically and based on laboratory data. Patients will be encouraged to report AEs/SAEs at the earliest recognition via the phone between the visits.
- m: Includes the analysis on Cycle 3, day 1. Only a decrease in tumor markers that met inclusion criteria at baseline may be used for randomization purposes.
- n: End of Treatment visit is to occur 30 days after the last dose of TKI therapy (or within 30 days of being removed from treatment in the case of adaptive therapy patients) \pm 7 days. The optional research biopsy may be taken up to 30 days after this visit as scheduling may require. If the subject is unable or unwilling to return to clinic this visit can be conducted via a telephone call.

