8. ASSESSMENT OF SAFETY

8.1 SPECIFICATION OF SAFETY PARAMETERS

Study participants will be monitored closely based on clinical, laboratory and imaging studies as outlined in study calendar (Table 8). Lenvatinib, Sorafenib, Cabozantinib and Vandetanib AEs and SAEs have been well described in literature (9-12). Patients will be educated and encouraged to report any AEs and SAEs promptly. Our primary endpoints include evaluation of safety and toxicity of adaptive TKI therapy and its comparison to conventional TKI therapy by measuring incidence of AEs and SAEs and time to its developments in adaptive and conventional therapy arms.

All AEs and SAEs will be graded according to CTCAE v5.0 (Appendix 3) and recorded in patient's charts and CRFs.

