8.4 REPORTING PROCEDURES

8.4.1 ADVERSE EVENT REPORTING

All AEs occurring prior to initiation of TKI therapy do not need to be reported.

All AEs occurring after first administration of TKI therapy (Lenvatinib, Sorafenib, Cabozantinib, or Vandetanib) and 30 days after last administration of TKIs will be considered as on treatment. All AEs will be collected and graded according to CTCAE v5.0 (Appendix 3), with the exception of Grade 1 laboratory abnormalities which will not be collected. All Grade 2 and above toxicities will be collected and documented by the investigator, but only Grade 3 toxicities deemed possibly, probably or definitely related to the study treatment will be reported on the appropriate CRFs/SAE reporting forms. Only SAEs will be reported to the PI. All AEs, including those persisting after end of study treatment must be followed up until they have resolved or have been sufficiently characterized or the principal investigator decides to not further pursue them.

Serious and non-serious AEs occurring later than 30 days after last administration of trial drugs will only be reported in case they are considered drug-related or trial (procedure) related.

Deaths (unless they are considered drug-related or trial related) will not be reported as SAE when they occur later than 30 days after last administration of the trial.

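### For patients who stop before 24 months, the End of Treatment safety visit is tied to the last dose in the conventional arm but only to removal in the adaptive arm, so adverse-event ascertainment after the last dose differs by arm

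*Combined protocol and SAP*

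**What the plan says.** Section 7.3.5 defines who has the visit: "An End of Treatment (EOT) visit will be performed for all subjects who do not complete the 24 month treatment period for any reason". Its timing is "30 days after last TKI dose, or any time within 30 days of being removed from treatment for patients in the adaptive therapy arm". The visit covers vital signs, physical examination, laboratory tests, urine dipstick, AE and SAE review, compliance and survival.

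Table 8 note n (Section 7.3.7) gives the same rule. After the 30-day timing it adds "or within 30 days of being removed from treatment in the case of adaptive therapy patients", applies a margin of plus or minus 7 days, and lets the visit be held by telephone if the patient cannot or will not return.

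Section 8.4.1 sets one AE window for everyone: events from the first dose up to "30 days after last administration of TKIs will be considered as on treatment".

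Section 8.1 describes the primary endpoints as including a comparison of safety by "measuring incidence of AEs and SAEs and time to its developments in adaptive and conventional therapy arms".

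**The concern.** Under the base rule the visit falls at about the day the AE window closes, so a scheduled assessment looks back over the whole window. The adaptive-arm option is anchored to removal, has no lower limit, and is not restricted to patients already off drug. An adaptive patient who is taking TKI when removed, including one removed for toxicity under Section 5.4.1, can have EOT on the day of removal. The window then runs with no further scheduled AE assessment.

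The events most exposed are new ones with no symptoms, such as laboratory or urine findings. The days after the last dose are not empty of drug for every agent. Section 6.1.8.2 gives vandetanib a 19-day half-life; with first-order elimination, 0.5^(30/19) = 0.33, so about a third remains at day 30.

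At stake is the between-arm safety comparison. With 24 and 12 randomized patients planned (Section 10.1), a few events found in one arm and not looked for in the other could change how it reads.

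**Working it through.** The plan states no figure on this point, so there is none to reproduce. The check is day arithmetic.

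**Inputs**
- AE window: 30 days after the last dose, both arms (Section 8.4.1).
- EOT, base rule: day 30 after the last dose (Section 7.3.5), margin 7 days (note n), so days 23 to 37.
- EOT, adaptive option: day 0 to day 30 after removal, or to day 37 with the margin.
- Assumption: for an adaptive patient on TKI at removal, the removal date is the date of the last protocol dose.

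**Formula.** With day 0 as the last dose and the visit on day d, days left uncovered = max(0, 30 − d).

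**Range**
- Conventional: d = 23 gives 7; d ≥ 30 gives 0. Range 0 to 7 days, at most 7/30 = 23% of the window.
- Adaptive, on TKI at removal: d = 0 gives 30; d ≥ 30 gives 0. Range 0 to 30 days, up to 100% of the window.
- Adaptive, already off TKI for k days at removal: the earliest visit is day k, so at most 30 − k days are uncovered. For k ≥ 30 the window has closed and nothing is uncovered.

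**Mean, assuming visits spread evenly over the allowed days**
- Adaptive, on TKI at removal, days 0 to 37: (30²/2)/37 = 450/37 = 12.2 days.
- Conventional, days 23 to 37: (7²/2)/14 = 24.5/14 = 1.75 days.
- Ignoring the margin in both arms: 450/30 = 15 days against 0.

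**Does anything else schedule a later look?**
- Section 5.4.2: patients who stop early are "followed for response until progression and for survival for 1 year from the date of withdraw or termination". Those removed for unacceptable AEs are followed until the event resolves or stabilizes. The first is not an AE assessment; the second follows a known event and does not search for new ones. The same section promises every effort at the safety follow-up the protocol specifies, but the only safety visit specified after an early stop is EOT.
- Table 8 note l: "Patients will be encouraged to report AEs/SAEs at the earliest recognition via the phone between the visits". This depends on the patient noticing something.
- Section 7.3.6: unscheduled visits happen only when something prompts them.

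None of these is a scheduled, active check for new AEs between an early EOT and day 30.

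**The case against.** The strongest reply is that the contrast is narrower than it looks.

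- **The rule is permissive and covers early stops only.** An adaptive patient may still be seen at day 30, and patients who complete 24 months have the Final Study Visit (Section 7.3.4), which has no post-dose timing in either arm. This stands and limits the scope.
- **Day-30 laboratory work is not guaranteed for conventional patients.** Note n permits a telephone EOT in either arm. This stands. The difference is in the timing of the scheduled assessment, not in an assured set of tests.
- **AE collection continues without visits.** The formal window is the same in both arms, and patients can phone. Section 8.4.1 does not collect Grade 1 laboratory abnormalities, and Section 10.3 specifies no between-arm AE test. This reduces the consequence, but Section 8.1 still announces the comparison.
- **Removal may be a deliberate anchor.** Sections 4.1 and 6.1.8 let adaptive patients go on to continuous TKI after progression, so removal from protocol treatment need not end dosing. This stands, and a correction has to deal with that group.

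A reader might infer two further things that the documents do not support. One is that the rule makes adaptive therapy look safer overall. Table 8 schedules ECOG status, vital signs and physical examination more often in the adaptive arm after cycle 3, and Section 7.3.3 adds 28-day visits while those patients are off drug. Ascertainment over the whole trial could therefore differ in either direction. The other is that the exception was intended only for patients already off drug. That is plausible, but no section states the purpose.

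**Conclusion.** The point holds in a limited form. The written rule allows active AE ascertainment after the last dose to differ by arm, by up to 30 uncovered days against up to 7. The exact limits follow from the text once removal is taken as the last-dose date for patients on TKI. The means of about 12 and 2 days rest on the even-spread assumption and only illustrate the gap.

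The number of patients affected is unknown, because the plan gives neither the number of early stops nor the share on TKI at removal. As an illustration, if 25% to 75% of adaptive early stops were on TKI and the rest had a closed window, the mean over all adaptive early stops would be 0.25 × 12.2 = 3.0 to 0.75 × 12.2 = 9.1 days.

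The shortfall in active assessment within the post-dose window is on the adaptive side; no net bias for the trial can be claimed. The primary time-to-discontinuation event precedes this visit and is not affected. The point should be corrected because it is an avoidable asymmetry in a planned comparison.

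**What to change.** Reconcile Section 7.3.5, Table 8 note n and Section 8.4.1 on three points:

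1. For patients still within 30 days of their last protocol TKI dose at removal, give the last AE assessment the same timing relative to that dose in both arms.
2. Keep the removal-based option for adaptive patients whose 30-day window has already closed.
3. State how patients who go straight on to off-protocol continuous TKI are handled: which dose counts as the last, and to which treatment later events are attributed.

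The cost is a wording change to the visit rule in two places plus the statement in point 3, with no added visit, test or staff. The downside is that the EOT date moves later for some adaptive patients.
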